## Study protocol

**Participants:** Young (18-39 years) and older ( $\geq 65$  years) participants will be recruited from the greater Dallas-Fort Worth metropolitan area. Exclusion criteria will include: 1) known heart disease or other chronic medical conditions currently requiring regular medical therapy such as cancer, diabetes, uncontrolled hypertension, or uncontrolled hypercholesterolemia; 2) currently taking tricyclic antidepressants, loop diuretics, centrally acting calcium channel blockers, or beta-blockers; 3) abnormalities detected suggestive of provable ischemia, undetected cardiac disease, or resting left bundle branch block on screening electrocardiogram; 4) current smoker or regularly smoked within the past three years, 5) body mass index greater than or equal to  $30 \text{ kg/m}^2$ ; 6) known gastrointestinal issues such as Crohn's disease or ulcerative colitis, and 7) pregnant (confirmed in young females using a urine pregnancy test).

**Study design and experimental controls:** Enrolled participants will complete a thermoneutral control visit and a hyperthermia trial. Participants will adhere to the following pre-test guidelines: not use non-steroidal anti-inflammatory drugs for at least 1 week, antibiotics for at least 3 weeks, and steroids for at least 6 weeks prior to enrollment and regular/ongoing use of supplements known to influence the intestinal barrier (i.e., probiotics, glutamine, bovine colostrum, etc.). All testing will take place between 8:00 and 9:00 AM after an overnight fast. Additionally, participants will be asked to refrain from aerobic/resistance exercise for 24 hours, alcohol for 24 hours, and caffeine for 8 hours prior to testing.

**Control visit:** Participants will ingest the multi sugar drink (described in detail below) dissolved in 100 mL of water for determination of resting (baseline) intestinal permeability. They will be asked to collect their urine for 3 hours into 3-L opaque polypropylene containers. During this time participants will remain rested (seated with minimal movement). Collected urine samples were then measured for volume and mixed well before two 1.5 mL aliquots will be taken and stored at  $-80^{\circ}\text{C}$ .

**Hyperthermia trial:** Upon arrival, participants will confirm adherence to the pre-test guidelines and voided their bladder into a polypropylene container to confirm euhydration and to calculate their baseline urine flow rate. Two 1.5 mL aliquots will be taken and centrifuged at  $20,800 \times g$  for 15 minutes in  $4^{\circ}\text{C}$ . 1 mL of each supernatant will be stored

at  $-80^{\circ}\text{C}$ . Before instrumentation, participants' body mass was measured using a precision balance scale with  $\pm 10$  g accuracy (Mettler Toledo, OH). Core temperature will be measured using an orally ingestible telemetric pill (e-Celsius performance pill  $\text{R}$ , BodyCap $\text{C}$ , Caen, France) taken no less than 1 hour before the baseline period. Mean skin temperature will be obtained as the weighted average of local temperatures measured via thermocouples attached to the skin surface on the chest (30%), arm (30%), anterior thigh (20%), and calf (20%). Heart rate will be obtained from an electrocardiogram (GE Medical Systems, Madison, WI). Blood pressure will be measured by using an arm cuff with a microphone placed over the brachial artery to detect Korotkoff sounds triggered from the ECG signal (Tango M2 Stress Test Monitor, SunTech Medical). Following instrumentation, participants will don a tube-lined suit that covered the entire body except for the head, hands, and feet. To manipulate core and skin temperatures participants will exercise on a cycle ergometer (Lode Corival Recumbent, Netherlands) at 20 watts while the temperature of the water circulating through the tube-lined suit will be increased and maintained at  $50^{\circ}\text{C}$ . When core temperature is increased by  $0.5^{\circ}\text{C}$  above baseline, participants will ingest the multi sugar drink dissolved in 100 mL of water, heated to core temperature, for assessment of intestinal permeability (described in detail below). Participants will be heated to thermal tolerance which was defined as: 1) a core temperature increase of  $2^{\circ}\text{C}$ , or 2) the time at which the participant expressed that they were unable to continue or had sustained symptoms of presyncope. After thermal tolerance is reached, the temperature of the water perfusing the tube-lined suit will be reduced to cool the participant. After a brief period of cooling, participants will towel off and measure their nude body mass. Participants will then drink at least 500 ml of water but remain rested and fasted for the remainder of the trial. Any urine produced for the 3 hours following ingestion of the multi sugar drink will be collected into 3-L opaque polypropylene containers. Collected urine samples will be measured for volume and mixed well before two 1.5 mL aliquots are taken and centrifuged at  $20,800 \times g$  for 15 minutes in  $4^{\circ}\text{C}$ . 1 mL of each supernatant will be stored at  $-80^{\circ}\text{C}$ .

**Blood sampling and analysis:** Blood samples will be collected through venipuncture of an arm vein into heparin, ethylenediaminetetraacetic acid (EDTA), or serum separator Vacutainers $\text{R}$  in the seated upright position prior to heating (baseline) and at the point of

thermal tolerance (end). We will measure hematocrit (microcapillary technique) and hemoglobin (ABL90 Flex, Radiometer, Brønshøj, Denmark) to calculate changes in plasma volume (Dill & Costill, 1974). Blood samples will be centrifuged to isolate plasma/serum and aliquots stored at -80°C for later analyses. We will measure plasma (heparin) intestinal fatty acid binding protein (I-FABP), plasma (EDTA) lipopolysaccharide binding protein (LBP), and plasma (EDTA) soluble cluster of differentiation 14 (sCD14) using enzyme-linked immunosorbent assays. In addition, to assess changes in renal function we will measure plasma (heparin) creatinine (Medica RA chemistry analyzer) and cystatin C (Tosoh AIA-360). Stored serum samples will be assayed using a chemo/cytokine multiplex assay (LHC0009M ThermoFisher Scientific, Waltham, MA) run on a Luminex™ MAGPIX platform (xMAP Technology, San Diego, CA).

**Urine analysis:** Stored urine samples will be assayed for tissue inhibitor of metalloproteinase 2 (TIMP-2) insulin like growth factor binding protein 7 (IGFBP7), neutrophil gelatinase-associated lipocalin (NGAL), and kidney injury molecule-1 (KIM-1) via enzyme-linked immunosorbent assays (RayBiotech Life, Peachtree Corners, GA). Urinary biomarkers will be normalized to urine flow rate.

**Multi sugar drink:** Intestinal permeability will be assessed using a multi sugar drink test as described elsewhere (van Wijck *et al.*, 2013). The drink will be modified to include only 1 g of lactulose (Kristalose®, Cumberland Pharmaceuticals, Nashville, TN), 1 g of sucrose (107653, Sigma-Aldrich, St. Louis, MO), and 0.5 g of L-rhamnose (W373011, Sigma-Aldrich, St. Louis, MO). The urinary recovery of each ingested sugar (lactulose, sucrose and rhamnose) will be determined by multiplying the measured concentration of each sugar by the total volume of urine collected and dividing by the dose administered. If lactulose or sucrose is not detected in the sample, the L/R ratio or sucrose excretion will be assumed to be 0.

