Impact of Aging on Gastrointestinal Permeability During Hyperthermia

Statistical Analysis Plan

NCT05816551

October 7, 2024

Statistical Analysis Plan: Data will be assessed for model assumptions (i.e., normality, equality of variance) and inspected for influential data points. Non-normally distributed data will be transformed using a log base 10 transformation. Data will be analyzed using linear mixed effect models with main effects of time or trial (within factor) and group (between factor; older vs young) or unpaired t-tests, as appropriate. Statistical significance was set a priori to $p < 0.05$.

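### Neither recruitment nor the analysis controls sex, so older-vs-young comparisons of levels can partly reflect a different sex mix in the two age bands

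*Protocol*

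**What the plan says.** The Participants paragraph of the protocol defines the groups by age and states that "participants will be recruited from the greater Dallas-Fort Worth metropolitan area". Seven exclusions then apply to both groups. They cover disease, medication, ECG findings, smoking ("current smoker or regularly smoked within the past three years"), a BMI of 30 or above, gastrointestinal disease and pregnancy. Sex appears only in the last of these: "pregnant (confirmed in young females using a urine pregnancy test". Women are therefore eligible, but no target ratio, quota, matching or stratified recruitment is described.

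On design, the protocol says that "Enrolled participants will complete a thermoneutral control visit and a hyperthermia trial". Trial is thus a within-person factor and age group a between-person factor.

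The SAP fits mixed models with "main effects of time or trial (within factor) and group (between factor; older vs young) or unpaired t-tests, as appropriate". No sex term or other covariate is named, and an unpaired t-test cannot take one.

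**The concern.** The trial asks about the impact of aging, and age group is observed, not assigned. Comparability then has to come from whom the study recruits or from what the analysis adjusts for. For sex, the documents provide neither.

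Nothing guarantees that volunteers aged 18-39 and volunteers aged 65 or above have the same proportion of women. If the proportions differ and a marker's level differs between men and women, the older-vs-young difference in level combines an age effect with a sex effect. The planned analysis cannot separate them. Plasma creatinine is a plausible example, because it depends on muscle mass. More participants do not cure a systematic difference of this kind: the bias stays the same size while the standard error shrinks.

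**Working it through.** **Plan's own figure.** There is none to reproduce. The documents give no sample size, power, SD, sex split or sex effect. The only numerical input is the significance level of 0.05, with sidedness not stated; two-sided is assumed here. All other inputs below are assumptions.

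**Step 1: which contrasts are exposed.** Let Δp be the difference between the age groups in the proportion of women. Let δ be the sex difference in a marker before heating, and λ the extra sex difference after heating (sex-by-time). The sex contribution to each contrast is:

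- older vs young, level before heating: δ × Δp
- older vs young, level after heating: (δ + λ) × Δp
- group main effect, averaged over both times: (δ + λ/2) × Δp
- older vs young, change from before to after: (δ + λ) × Δp − δ × Δp = λ × Δp

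The same holds with trial (control vs hyperthermia) in place of time. If λ = 0 on the scale analysed, the level contrasts carry δ × Δp and the difference in change carries nothing. The heating effect itself is estimated within persons, so a sex difference between the groups does not confound it.

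**Step 2: size under a systematic difference.** Assume a within-sex SD of 1, λ = 0, no true age effect, and proportions of women p1 and p2.

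- Bias = δ × (p1 − p2)
- Within-group variance v = 1 + δ² × [p1(1 − p1) + p2(1 − p2)]/2
- Noncentrality = bias / √(2v/n), with 2n − 2 degrees of freedom

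Worked case, δ = 0.5, 70% vs 30%, n = 20 per group: bias = 0.5 × 0.4 = 0.20 SD; v = 1 + 0.25 × 0.21 = 1.0525; noncentrality = 0.20/√0.10525 = 0.616. The two-sided test at 0.05 then rejects with probability 0.092.

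| Sex effect (SD) | Women, p1 vs p2 | Bias (SD) | False-positive rate, n = 10 | n = 20 | n = 30 |
|---|---|---|---|---|---|
| 0.3 | 60% vs 40% | 0.06 | 0.052 | 0.054 | 0.056 |
| 0.5 | 70% vs 30% | 0.20 | 0.070 | 0.092 | 0.115 |
| 0.8 | 70% vs 30% | 0.32 | 0.098 | 0.153 | 0.208 |

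The rate rises with n because the bias does not shrink.

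**Step 3: chance imbalance is a different matter.** Suppose both bands are drawn from pools with 50% women. From two independent binomials, the chance that the observed proportions differ by 20 points or more is 0.503, 0.362, 0.268, 0.203 and 0.155 for 10, 15, 20, 25 and 30 per group. Imbalance of this size is common in small groups. But sex is then part of the ordinary within-group variance, which the t-test already counts. A simulation of this setting (100,000 runs per cell, sex effect 0.5 or 1.0 SD, 10, 20 or 30 per group, no age effect) gave false-positive rates between 0.049 and 0.051. Chance imbalance makes a single dataset harder to interpret; it does not raise the error rate.

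**The case against.** The case against has three parts, and much of it stands.

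First, a reader might infer from the frequency of chance imbalance that the planned tests are biased or reject too often. The documents do not support that, and Step 3 shows that it does not follow. Bias needs age bands whose sex mix differs systematically. The protocol neither reports nor rules out such a difference.

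Second, a reader might infer that the main question, how aging alters the response to heat, is confounded by sex. A constant sex offset cancels from within-person change and from the older-vs-young difference in change, and nothing in the documents indicates that sex modifies the response. Creatinine is measured to follow changes in renal function, so a stable muscle-mass offset drops out there. The 20 W workload is the same for everyone, but the sugar drink is timed to each person's 0.5°C rise, and heating ends at a 2°C rise or at tolerance. Exposure is thus tied largely to the individual's own core temperature. The documents also offer no sex mechanism for the sugar-recovery or gut-barrier markers.

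Third, recruitment is not unrestricted apart from age: health, medication, smoking and BMI are limited in both groups. The gap concerns sex.

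What these objections leave untouched is the comparison of levels. The SAP names group as a main effect ("group (between factor; older vs young") and allows unpaired t-tests, and where either is applied to levels the sex difference does not cancel. The SAP does not spell out the interaction in which it would.

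**Conclusion.** The point holds for comparisons of levels between age groups, meaning group main effects and unpaired t-tests on levels. There, a systematic difference in sex mix would enter the age contrast uncorrected. Older-vs-young differences in the response to heat are affected only if sex modifies that response. Within-person heating effects are not confounded by sex.

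The size cannot be stated from the documents. Under the assumed sex effects and splits, the shift runs from 0.06 to 0.32 SD; these values illustrate the mechanism and do not estimate it. They rest on an additive sex effect, opposite 60:40 or 70:30 splits, and 10 to 30 participants per group. It would be wrong to read the point as showing that the groups are in fact unbalanced, or that the planned tests have an inflated error rate as they stand.

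The point deserves action because the age contrast is the purpose of the study and the remedy is cheap.

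**What to change.** **If enrollment is open.** State in the Participants paragraph that recruitment aims for the same proportion of women in each age group by the end of enrollment. The rule should concern proportions: 10 women of 15 (67%) and 10 of 20 (50%) have equal counts but are not balanced. Setting the target for the end of enrollment lets the two bands recruit at different speeds. With equal proportions, Δp = 0 and the bias from an additive sex effect is zero. Cost: a running tally, and perhaps a few late volunteers of the over-represented sex declined.

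**If enrollment is complete.**

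- Report the sex split by age group.
- Add sex as a fixed effect to the mixed models, and replace the unpaired t-tests with linear models containing group and sex.
- State in advance whether the adjusted or the unadjusted result is primary. Showing both without naming one leaves two answers to choose from. If group results have already been seen, say so.
- For group-by-time or group-by-trial contrasts, add a sex-by-time or sex-by-trial term as a sensitivity analysis. A sex main effect alone does not serve here: with complete data it leaves those estimates unchanged.

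Cost: one or two degrees of freedom, plus some precision if sex and age group are correlated. With equal groups at 70% vs 30% women, that correlation is (0.25 × 0.4)/0.25 = 0.4, and the variance of the group effect is multiplied by 1/(1 − 0.4²) = 1.19. This is partly offset by the variance that sex explains.

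### Does the plan need a rule for correcting the blood markers for plasma-volume change?

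*Protocol*

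**What the plan says.** Under Blood sampling and analysis, the protocol has blood drawn "in the seated upright position prior to heating (baseline) and at the point of" thermal tolerance. Hematocrit and hemoglobin are measured "to calculate changes in plasma volume", by a cited published method. The same paragraph then lists the assays: "We will measure plasma (heparin) intestinal fatty acid binding protein (I-FABP), plasma (EDTA) lipopolysaccharide binding protein (LBP"), sCD14, and, "to assess changes in renal function we will measure plasma (heparin) creatinine" and cystatin C, followed by a serum cytokine panel. It does not say how the plasma-volume figure is used.

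Other measurements do have a rule. Under Urine analysis: "Urinary biomarkers will be normalized to urine flow rate". Under Multi sugar drink, recovery comes from "multiplying the measured concentration of each sugar by the total volume of urine collected", divided by the dose.

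The SAP is one paragraph. "Data will be analyzed using linear mixed effect models" with main effects of time or trial and of group, or with unpaired t-tests. It allows a log10 transformation and sets p < 0.05. It does not mention plasma volume.

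**The concern.** Heat stress can draw fluid out of the circulation. A marker that stays in plasma then becomes more concentrated even if none has been released, so an uncorrected rise from baseline to end mixes haemoconcentration with release. Under Hyperthermia trial, heating stops at a 2 °C rise in core temperature, or at "the time at which the participant expressed that they were unable to continue", or at sustained presyncope symptoms. Time under heat at the end draw is therefore not fixed, and the design does not force plasma-volume loss to be equal across participants or age groups.

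The urine measures have written rules and the blood measures have none, so an analyst could in principle look at corrected and uncorrected results and report the more attractive set. At stake would be claims that a blood marker rose with heating and, if losses differed by age, claims that it rose more in one age group.

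**Working it through.** **Inputs.** The documents give no plasma-volume loss, sample size or standard deviation, so there is no stated figure to reproduce. Assumed here: loss *d* of 5%, 10% or 15%; 10 to 20 participants per group; SD of the within-person change in the **natural** log of the marker from 0.10 to 0.50; two-sided 0.05. The SAP's transformation is log10, so log10 shifts must not be set against these SDs.

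**Size of the shift.** With circulating amount unchanged, the end concentration is multiplied by 1/(1 − d).

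| Loss | Rise, 1/(1 − d) − 1 | log10 shift | natural-log shift |
|---|---|---|---|
| 5% | 5.3% | 0.022 | 0.051 |
| 10% | 11.1% | 0.046 | 0.105 |
| 15% | 17.6% | 0.071 | 0.163 |

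**Time effect, uncorrected, no true release.** Non-central t with shift −ln(1 − d), SE = SD/√(2n) and df = 2n − 2. At d = 10%, SD 0.30 and n = 15 per group, SE = 0.30/√30 = 0.055 and the chance of p < 0.05 is 46%. Across the assumed range it runs from 7% (5% loss, SD 0.50, n = 10) to about 100% (10% to 15% loss, SD 0.10).

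**Does the choice of version change the result?** Simulated trials with n = 15 per group and individual loss of mean 10%, SD 3%. The table gives the share in which corrected and uncorrected analyses disagree on p < 0.05 for time.

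| SD of log change | True rise 0% | 5% | 10% | 20% |
|---|---|---|---|---|
| 0.10 | 95% | 27% | 0% | 0% |
| 0.30 | 46% | 64% | 55% | 10% |
| 0.50 | 20% | 30% | 40% | 38% |

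There is no stable pattern. At SD 0.10 the choice matters only for small true rises. At SD 0.50 it matters more for a 20% rise than for none. The documents do not say which row applies.

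**Age comparison.** Equal losses cancel in the ratio of end to baseline. If one group loses 10% and the other 5%, the ratios differ by 0.95/0.90 − 1 = 5.6%. A test of difference in change (SE = SD√(2/n)) would be significant in 6% to 39% of trials, and in 8% at SD 0.30 with n = 15. That is a group-by-time interaction, which the SAP does not list. The listed group main effect averages the two draws and shifts by √1.056 − 1 = 2.7%. Taking 0.10 to 0.50 as the between-person SD of that average, it is significant in 5% to 13% of trials, and in 5.7% at SD 0.30 with n = 15.

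**Permeability test.** Sugar recovery is urine concentration times urine volume over dose. No plasma concentration enters it, so the issue does not reach it.

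**The case for a change.** The best case for a change is that intent does not settle the detail. Even if correction is meant, the plan does not say which markers it covers or which version leads, and the answer may differ by marker: creatinine and cystatin C are read as concentrations for renal function, I-FABP as a sign of release. Leaving this open has a price. At 10% loss, SD 0.30 and 15 per group, with no true rise, the chance that at least one version reaches p < 0.05 for time is 48%, against 5% if correction is fixed in advance. Writing the rule down would be cheap, since the measurements are already planned.

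The omission stands, and so does the arithmetic. But the 48% supposes an analyst who computes both versions and picks, which nothing in the documents suggests. The point about creatinine also cuts the other way. If concentration is the target, the uncorrected value is not biased, so the plan's silence cannot be called an error without first choosing the target for each marker. The request is then for a fuller description, and it does not itself select a version.

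**Conclusion.** No change to the plan follows. This is missing detail that analysts can be expected to fill sensibly. The plan states no wrong rule, it collects what correction needs, and it places the calculation where correction is the obvious use. Once the plasma-volume change is known the formula is simple: end value × (1 + fractional change). Whether to apply it to a given marker is a fair trade-off, because correction targets circulating amount rather than concentration and adds some measurement error.

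The possible effect is 5.3% to 17.6% on uncorrected end values for assumed losses of 5% to 15%, and it bears mainly on the time effect of the blood markers. The age comparison of change on the log scale moves only if losses differ by age. Even with an assumed 10% versus 5% split, the listed group main effect moves by 2.7%. The urinary sugar test of permeability, the subject of the SAP's title, is untouched. All losses, SDs and group sizes here are assumptions. Stating in the report which markers were corrected, with plasma-volume change by age group, would be good documentation, but the analysis does not depend on a change to the plan.

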Impact of Aging on Gastrointestinal Permeability During Hyperthermia

Statistical Analysis Plan

NCT05816551

October 7, 2024

Statistical Analysis Plan: Data will be assessed for model assumptions (i.e., normality, equality of variance) and inspected for influential data points. Non-normally distributed data will be transformed using a log base 10 transformation. Data will be analyzed using linear mixed effect models with main effects of time or trial (within factor) and group (between factor; older vs young) or unpaired t-tests, as appropriate. Statistical significance was set a priori to $p < 0.05$.

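### As written, the SAP's mixed model has no age-by-heat term, so its group effect cannot tell an age difference under heat from one at rest

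*SAP*

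**What the plan says.** The SAP's statistical section is one paragraph. Its model sentence specifies "linear mixed effect models with main effects of time or trial (within factor) and group (between factor; older vs young"), and offers unpaired t-tests as an alternative where suitable, without tying them to any outcome, visit or derived value. It adds: "Non-normally distributed data will be transformed using a log base 10 transformation". Its title is "Impact of Aging on Gastrointestinal Permeability During Hyperthermia".

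The Protocol describes a paired design: "Enrolled participants will complete a thermoneutral control visit and a hyperthermia trial". The sugar test is done at both visits. Blood is drawn twice at the hyperthermia visit, once "in the seated upright position prior to heating (baseline") and once at thermal tolerance. The Multi sugar drink section sets the lactulose/rhamnose (L/R) ratio to 0 when lactulose is undetected, and sucrose excretion to 0 when sucrose is undetected.

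For the urinary kidney markers the Protocol says only "Stored urine samples will be assayed for tissue inhibitor of metalloproteinase 2 (TIMP-2") and the other listed markers. Three urine samples are stored: the control-visit collection, the void on arrival for the hyperthermia trial, taken "to confirm euhydration and to calculate their baseline urine flow rate", and the later collection ("Any urine produced for the 3 hours following ingestion of the multi sugar drink will be collected").

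**The concern.** The title and the paired design suggest that the question is either the age difference under heat or the age difference in the response to heat. A model with only the two main effects imposes the same heat response on both age groups. Its trial or time term is the common response, and its group term is an age difference averaged over both conditions. Neither is the quantity of interest.

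Three situations would be misread from the group term alone. An age difference that exists only under heat is halved. A constant resting difference can be declared significant although both groups respond to heat identically. Differences of opposite sign at rest and in heat cancel.

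There is a separate difficulty with scale. Whether an interaction is present depends on whether the data are analysed raw or on log10. The SAP's log10 rule also cannot be carried out on sugar outcomes that contain the zeros the Protocol assigns.

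**Working it through.** **No planned figure to reproduce.** The documents give no sample size, SD, within-person correlation or effect size. The algebra in step 1 needs none of these. Steps 2 to 4 are illustrations under stated assumptions.

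**1. What each term estimates.** Let R and H be the older-minus-young differences at rest and in heat. With complete pairs and equal variances:

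- group term, main-effects model: (R + H)/2
- group-by-trial interaction: H − R
- age contrast within hyperthermia: H

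For a difference d, heat-only (R = 0, H = d) and rest-only (R = d, H = 0) both give a group term of d/2, while the interaction is +d and −d respectively. With R = −d and H = d the group term is 0. Missing values, or a model that lets variance differ by condition, move the weights away from one half, but the term remains a weighted average of R and H. In one simulated complete dataset with R = 0.652 and H = 1.271, the main-effects model returned 0.961, their average.

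**2. Size.** Assumed: n = 15 per group, SD 1 in each cell, correlation ρ = 0.5, two-sided 0.05, non-central t with 2n − 2 = 28 df. With k = √(2/n) = √(2/15) = 0.365, the standard errors are:

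- group term: k√((1+ρ)/2) = 0.365 × √0.75 = 0.316
- heat values alone: k = 0.365
- interaction: k√(2(1−ρ)) = 0.365 × √1 = 0.365

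In the heat-only case the group term has non-centrality 0.4/0.316 = 1.26 and the interaction 0.8/0.365 = 2.19. Rejection rates follow; brackets give the range over n = 10 to 20 and ρ = 0.3 to 0.7.

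| Older minus young, in SD | Group term | Heat values alone | Interaction |
|---|---|---|---|
| +0.8 at both visits | 69% [45–86] | 56% [40–69] | 5% |
| +0.8 in heat only | 23% [15–33] | 56% [40–69] | 56% [30–89] |
| +0.8 at rest only | 23% [15–33] | 5% | 56% [30–89] |
| −0.4 at rest, +0.4 in heat | 5% | 19% [14–23] | 56% [30–89] |

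A simulation of 40,000 datasets at n = 15 and ρ = 0.5 agreed: 69.1/56.5/4.9%, 23.0/55.9/56.1%, 23.1/5.0/56.1% and 5.0/18.6/55.9%, row by row.

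**3. Cost of the interaction in power.** For 0.8 SD in heat only at n = 15, heat values alone give 56% at any ρ. The interaction standard error is 0.365 × √1.4 = 0.432 at ρ = 0.3 (power 43%), 0.365 at ρ = 0.5 (56%) and 0.365 × √0.6 = 0.283 at ρ = 0.7 (78%).

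**4. Scale.** Assumed lognormal data, 15 per group, coefficient of variation 0.3 to 0.8, ρ = 0.3 to 0.7, with a t-test on within-person change. These data have SD proportional to the mean, so they are not the same setting as step 2.

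- Heat doubles values in both groups (young 1 to 2, older 1.5 to 3): rejection is 5% on log10 and 9–65% raw.
- Heat adds the same amount (young 1 to 2, older 1.5 to 2.5): rejection is 9–57% on log10 and 4–5% raw.

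A rank-sum test on raw change does not remove this dependence: in the doubling case it rejected about 8–61% of the time. For an undetected sugar, log10(0) is undefined, and the SAP gives no rule for it.

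**The case against.** The strongest reply is that the SAP does not rest on the group term alone. It also allows unpaired t-tests, and such a test on hyperthermia values, or on heat-minus-rest change, would answer the question directly. With complete pairs, the test on change is the same as the interaction test. This stands in part: the tool is available, but nothing assigns it to an outcome, a visit or a change score, so the choice stays open until the data are seen.

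Second, labelling one factor as within and the other as between describes a standard two-factor mixed design, and *main effects* may simply be naming its factors. If so, the defect is one of wording and the table does not describe the planned analysis. That reading is plausible but is not in the text.

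Third, the objective is inferred. The front matter of the Protocol was not available, and its absence is not held against the plan. The point needs only that age under heat, or age in the response to heat, is the target; the group term estimates neither.

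A reader might also infer that the kidney markers are compared between the pre-heating void and the 3-hour collection. The documents do not establish that. Control-visit urine is stored too, so a control-versus-hyperthermia comparison, or one using all three samples, fits the text equally well.

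**Conclusion.** The point holds as a gap in specification that should be closed. Followed literally, the mixed model has no term for an age difference in the heat response. With complete pairs and equal variances, its group effect gives the same expected value and rejection rate for a heat-only and an equal rest-only difference. Under the assumed 15 per group and correlation 0.5, a 0.8 SD difference in one condition is estimated as 0.4 SD and detected 23% of the time. These percentages are illustrative; the averaging itself does not depend on them.

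A reader might go further and conclude that the plan cannot answer its question, or that the interaction has been deliberately left out. The documents support neither: the t-test option could answer it, and the model wording may be shorthand. Confidence is medium for that reason. The conflict between the log10 rule and the assigned zeros is a separate defect and holds on either reading of the model.

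**What to change.** Replace the model sentence with wording such as:

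> Linear mixed effect models will include fixed effects of trial (or time), group and their interaction, with a random intercept for participant. The group-by-trial interaction (sugar recoveries, L/R ratio) or the group-by-time interaction (blood markers) tests the age difference in response. The older-versus-young difference within hyperthermia is reported as a model contrast with a 95% CI. For urinary kidney markers, the samples compared (control visit, pre-heating void, 3-hour collection) are stated and the matching interaction is used. Where an unpaired t-test is used, the outcome and the value tested (a single value or within-person change) are named. The analysis scale is stated in advance for each outcome; log10 is not applied to sugar outcomes containing zeros without a prespecified method that accommodates them.

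If the present wording was shorthand for a factorial model, the same change settles it.

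The cost is a rewritten sentence and one model degree of freedom, with no new data. The interaction has less power than heat values alone when within-person correlation is below 0.5 (43% against 56% at an assumed 15 per group, 0.8 SD and correlation 0.3), which is a reason to report the within-hyperthermia contrast beside it.
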